Appendix C: Interim Analysis and Sample Size Consideration

We plan to conduct formal interim analyses once 28-day PODS+death is available for one-third ($n=222$) and two-thirds ($n=444$) of the full study ($n=666$). Given the conflicting literature with regards to the direction a vitamin C effect, we plan for one-sided interim analyses which would suggest stopping for harm/futility if a signal increased PODS+death is observed in the vitamin C arm. We have examined the study characteristics of various stopping rules using 10,000 simulations for each treatment effect scenario. A relative risk (RR) of 1 equates to the null hypothesis, an $RR < 1$ favours Vitamin C, and in all scenarios, we assume a 27% 28-day PODS+death rate in the control arm. With 10,000 simulations, the estimates of all percentages will have at least a 95% chance of being estimated to within 1% and the mean RR and Bias have more than a 95% chance of being accurate to the second (and final) decimal reported. All simulations were analyzed according to the analysis plan by using modified Poisson regression clustering for site and controlling for: age, sex, ethnicity, TBSA burn, traumatic brain injury, mechanically ventilated at baseline and injury severity. However, the data generated assumed that each observation was independent, so that there was no clustering by site and none of the covariates were related to the outcome. It may be noted that the actual number of simulations is up to 0.7% less than 10,000. This is due to the generalized estimating equations (GEE) algorithm used for the modified Poisson model not converging. We chose the modified Poisson over the log-binomial model because the log-binomial model did not converge in over 30% of the simulations and we chose modified Poisson over logistic regression due to the preference of estimating relative risks rather than odds ratio.

We wanted to have a high probability of stopping at the interim if vitamin C was harmful, but a low probability of stopping if vitamin C was not harmful. We also wanted the stopping rule to cause minimal type I error inflation, minimal loss of power and minimal bias in the final estimate – which would come from the interim analysis if the study stopped early. Finally, we could not choose a rule that would guide the DMC to recommending continuing the study at an uncomfortably large RR. Based on these criteria and simulation results, we choose a stopping threshold of $RR > 1.1$ (in the direction of harm) regardless of statistical significance at either of two interim analyses. This stopping rule only trivially reduced power for detecting benefit of vitamin C and did not meaningfully increase the type I error compared to no interim analysis. The simulation results with this stopping rule are presented in table B. Under the null hypothesis, the $RR > 1.1$ stopping rule would have a 33.3% and 8% chance of stopping at the first and second interim respectively. The expected RR would be 1.08 (a bias of 0.08), but the 95% confidence intervals would contain the true value of one 94% of the time which is the same as obtained without a stopping rule. The trivial type I error inflation and corresponding sub-nominal 95% confidence interval coverage appears even without an interim analysis due to using the modified Poisson approach which uses robust standard errors. With the $RR > 1.1$ rule, if the true $RR=1.2$ there will be a 67% chance of stopping at the first interim, and a 14% chance of stopping at the 2nd interim. With a true $RR=1.333$ there would be an 83% and an 11% chance of stopping at the 1st and 2nd interim analysis respectively. Under the assumed effect size of $RR=0.666$ we would maintain 78% power with only a 1% chance of stopping a study early that would otherwise have gone on to be statistically significant.

In summary, the one-sided futility/safety stopping rule has only trivial impact on the study characteristics if vitamin C is meaningfully beneficial. However, if vitamin C is harmful, there is a high probability that the study will stop at one-third the way through the study which will greatly reduce the power to detect a statistically significant harm; also, this will slightly bias the RR towards greater harm, but the 95% confidence intervals will still maintain near nominal coverage of the correct RR. We believe this is a worthwhile trade-off to save patients from unnecessary harm and to save resources from being used to complete a study that had virtually no chance of detecting a significant benefit of vitamin C.

Table B: Operating Characteristics of Trial Under RR>1.1 Stopping Rule at 1/3 and 2/3 Enrollment

		Stopped at 1st interim (n=222) for futility/harm			Stopped at 2nd interim (n=444) for futility/harm			Completed study									
Control 28-day PODS Rate 27%	N	p>=0.05	p<0.05	Total	p>=0.05	p<0.05	Total	p>0.05	benefit at p<=0.05	harm at p<=0.05	Total	RR	Bias		Coverage of 95% CI	Average 95% CI Width	Stopped at Interim but would have shown significant benefit at final
		%	%	%	%	%	%	%	%	%	%	Mean	Mean	Std			
Scenario																	
I 18% RR=0.666	9929	2.7	0.0	2.7	0.1	0.0	0.1	19.1	78.1	0.0	97.2	0.68	0.02	0.13	92%	0.41	0.9%
I 20.25% RR=.75	9949	5.7	0.1	5.8	0.5	0.0	0.5	40.0	53.6	0.0	93.6	0.78	0.03	0.16	92%	0.46	0.6%
I 21.6% RR=.8	9964	9.7	0.3	10.0	1.0	0.0	1.0	50.8	38.2	0.0	89.0	0.84	0.04	0.18	91%	0.51	0.6%
I 24.3% RR=.9	9965	19.4	1.1	20.5	3.4	0.0	3.4	62.5	13.5	0.0	76.0	0.96	0.06	0.20	93%	0.61	0.3%
I 27% RR=1	9963	30.2	3.1	33.3	8.0	0.0	8.0	55.9	2.9	0.0	58.8	1.08	0.08	0.21	94%	0.72	0.0%
I 29.7% R=1.1	9962	41.5	8.1	49.6	12.2	0.0	12.2	37.5	0.4	0.2	38.1	1.19	0.09	0.21	94%	0.84	0.0%
I 32.4% RR=1.2	9969	51.2	16.2	67.4	13.8	0.0	13.8	18.3	0.0	0.6	18.9	1.29	0.09	0.23	94%	0.96	0.0%
I 33.75% RR=1.25	9958	51.6	21.9	73.5	13.4	0.0	13.4	12.6	0.0	0.4	13.0	1.33	0.08	0.24	95%	1.00	0.0%
I 36% RR=1.333	9948	50.6	32.1	82.7	11.4	0.0	11.4	5.2	0.0	0.6	5.8	1.40	0.07	0.26	95%	1.07	0.0%

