Once consent is obtained, and necessary baseline data collected for qualifying patients, the study co-ordinator will log on to the web-based randomization system at the Clinical Evaluation Research Unit at Queen's University. The system will confirm eligibility prior to allowing randomization. The system will then provide the study co-ordinator with a patient study number and who will then contact the local pharmacist or delegate with notification of randomization. The unblinded pharmacist or delegate will then access the system to determine the treatment assignment. Allocation will be random and concealed and will be blinded to everyone except the pharmacist at each site who will be responsible for preparing study samples and delivering them to the ICU in a blinded fashion in accordance with the documented study operating procedures. The randomization system, which has proven reliable in several prior RCTs, has a robust audit trail, and will maintain concealment and blinding.

The randomization system will use a computer-generated randomization schedule allocating patients 1:1 to either vitamin C or matching placebo by the method of permuted blocks of random undisclosed size stratified by centre. The study statistician will be responsible for generating the randomization codes and will keep these codes in a password protected file on a private drive on the servers at Kingston Health Science Center. Given the large pragmatic nature of the definitive trial, we will not stratify by additional factors such as burn severity. Since there are no antidotes to Vitamin C, there are no unblinding procedures. Study IP stopping rules are articulated in section 1.5.

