2.7 What is the proposed duration of follow-up?

Patient clinical status will be monitored daily during the acute care unit stay for up to 3 days after termination of study IP (maximum 7 days). Hospital outcomes will be abstracted from the chart once the patient is discharged.

2.8 and 2.9 What are the proposed primary and secondary outcome measures?

The primary outcome for this phase III trial is persistent organ dysfunction (POD)+death at 28 days, a novel composite endpoint that combines being alive and being free of organ support (inotropes or vasopressors or mechanical circulatory assistance, renal replacement therapy and mechanical ventilation).⁷⁷

The most important secondary endpoint of this trial will be “time to discharge alive from hospital.” The other secondary outcomes will be the components of 28-day POD which include mortality, use of inotropes or vasopressors or mechanical circulatory assistance, renal replacement therapy and mechanical ventilation and POD-free days in the first 28 days.

Tertiary outcomes will include intensive care unit (ICU) outcomes (e.g. length of stay, duration of mechanical ventilation, and readmission rates); hospital outcomes (hospital mortality, length of stay, bacteremia with gram-negative bacilli, and readmission rates); and 6-month outcomes (mortality, health related quality of life and physical function domain of the Short Form-36 (SF-36) questionnaire, activities of daily living and instrumental activities of daily living). We will also record frequency of operative procedures for burn care, presence of inhalation injury, blood transfusions, and other major cost drivers to support our economic evaluation.

2.10 What is the proposed sample size and what is the justification for the assumptions underlying the power calculation?

The primary outcome for this trial is PODS+death at 28 days after randomization. Based on estimates from currently available pooled data from the RE-ENERGIZE study with $\geq 20\%$ TBSA (n=539), we estimate that the 28-day PODS rate will be 27%. Based on our simulations accounting for two interim analyses (see Tables in Appendix C), we estimate that with 333 subjects per arm, we would achieve 78% power to observe a reduction at a one-sided alpha of 0.025 (or two-sided alpha=0.05) if the rate of PODS at 28 days was reduced from 27% to 18% (RRR=33.3%).

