2.16 What is the statistical and data analysis plan?

In accordance with the intent-to-treat (ITT) principle, the analysis will include all patients in the arm to which they are randomized regardless of study compliance except patients who do not receive any of the study intervention (modified ITT analysis). In addition, we will conduct a per-protocol analysis of all truly eligible patients who receive all 16 doses. All of the analysis, including reporting of participant flow and patient characteristics by arm, will be presented in accordance with the CONSORT statement. Our primary outcome (alive and PODS free at 28 days) will be compared between groups using by an adjusted relative risk estimated by a modified Poisson regression with robust standard errors clustering by site and controlling for the following baseline covariates: TBSA burn, traumatic brain injury, mechanically ventilated at baseline and injury severity score.⁸⁰ This approach will meet regulatory guidance and best practices suggesting that site and strongly predictive baseline covariates be considered for adjustment in the analysis of multicenter studies.⁸¹⁻⁸³ Binary secondary outcomes will be analyzed similarly.

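### The 78% power in section 2.10 goes with an actual one-sided error of about 0.029, not 0.025; section 2.16 should name a small-sample correction for the site-clustered variance

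*Combined protocol and SAP*

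**What the plan says.** Section 2.16 sets the primary analysis as an adjusted relative risk from "modified Poisson regression with robust standard errors clustering by site", with four baseline covariates. Binary secondary outcomes are handled the same way. No small-sample correction and no reference distribution are named.

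Section 2.10 gives the power without a caveat: "we estimate that with 333 subjects per arm", "we would achieve 78% power to observe a reduction at a one-sided alpha of 0.025", for 27% against 18%. It refers to Appendix C for the simulations.

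Appendix C describes those simulations. Patients are independent, there is no site effect, and none of the covariates (seven there) predicts the outcome. The number and sizes of the simulated sites are not given. The results are in "Table B: Operating Characteristics of Trial Under RR>1.1 Stopping Rule at 1/3 and 2/3 Enrollment":

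- RR 0.666: significant benefit in 78.1% of runs, coverage 92%.
- RR 1: significant benefit in 2.9% of 9,963 runs, coverage 94%.

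The text comments: "The trivial type I error inflation and corresponding sub-nominal 95% confidence interval coverage appears even without an interim analysis". It attributes this to the modified Poisson approach with its robust standard errors, treats it as trivial, and changes nothing.

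**The concern.** Power and error rate come from the same simulation, but section 2.10 pairs the simulated power with the nominal alpha instead of the simulated one. The excess favours claims of benefit: 0.029/0.025 = 1.16, a relative inflation of about 16% in the confirmatory error rate.

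The stated cause matters too. If the inflation came with modified Poisson regression as such, accepting it would be the price of estimating a relative risk. If it comes from a clustered sandwich with few clusters, there is a standard remedy, and the size of the problem depends on how many sites contribute data.

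**Working it through.** **Inputs.** 333 per arm, 27% v 18%, one-sided 0.025 (section 2.10); 1:1 allocation in permuted blocks within centre (section 2.3); stop at 222 or 444 patients if the adjusted RR exceeds 1.1 (section 2.16); at least 40 sites planned (section 2.15); independent data, non-prognostic covariates (Appendix C). Assumed, because the documents are silent: 40 simulated sites (range 20–60), site sizes and block size.

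**1. Reproduce the 78%.** SE(log RR) = √[0.73/(333×0.27) + 0.82/(333×0.18)] = √(0.00812 + 0.01368) = 0.1476. Power = Φ(ln 1.5/0.1476 − 1.96) = Φ(0.786) = 78.4%. A pooled two-proportion test gives 79.6%. Table B puts the loss from stopping at 0.9 points, which leaves 77.5–78.7%. The printed 78.1% is reproduced.

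**2. Is 2.9% noise?** SE = √(0.025×0.975/9,963) = 0.00156, so z = 0.004/0.00156 = 2.6. The 95% CI around 2.9% is 2.57–3.23%. Over the rounding range 2.85–2.95%, z is 2.2–2.9. A rule that stops only for harm cannot create false benefit. Rejections in both directions sum to 3.1 + 0.0 + 2.9 + 0.0 = 6.0%, which agrees with the printed 94% coverage.

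**3. Size-adjusted power from Table B alone.** Φ[z(0.781) + z(0.971) − 1.96] = Φ(0.776 + 1.896 − 1.960) = Φ(0.711) = 76.2% (75.9–76.4% over the rounding range).

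**4. Cause.** Re-simulation of Appendix C's design with 40 sites, seven null covariates, and about 10,000 runs at each RR. False benefit and power include the stopping rule. The simulation SE of a 2.5% rate is about 0.16 points.

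| Variance, reference | False benefit, RR 1 | Power, RR 0.667 | Null coverage, no stopping |
|---|---|---|---|
| Table B and Appendix C text | 2.9% | 78.1% | 94% |
| Site-clustered sandwich, normal | 2.94% | 78.7% | 94.2% |
| Site-clustered sandwich, t on 39 df | 2.65% | 76.9% | 94.9% |
| Mancl-DeRouen, normal | 2.57% | 76.6% | 95.0% |
| Mancl-DeRouen, t on 39 df | 2.29% | 74.7% | 95.7% |
| Robust, not clustered, normal | 2.56% | 78.5% | 95.1% |

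The uncorrected clustered row matches the protocol's figures. The last row keeps modified Poisson and robust standard errors but drops the clustering, and the excess disappears. In further runs, G/(G−1) with t on sites−1 df gave 2.5–2.6% false benefit and 75.8–76.9% power. The uncorrected version gave 3.4% with 20 sites and 2.85% with 60 (8,000 runs each). With the four covariates of section 2.16 in place of seven it gave 2.96%.

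**5. Coverage in the benefit rows** (without / with the stopping rule):

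| True RR | Table B | Uncorrected | Mancl-DeRouen, normal |
|---|---|---|---|
| 0.667 | 92% | 94.2% / 92.7% | 95.0% / 93.7% |
| 0.8 | 91% | 94.1% / 91.8% | 94.9% / 93.2% |

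The variance estimator costs about 1 point. The stopping rule costs 94.2 − 92.7 = 1.5 points at RR 0.667 and 94.1 − 91.8 = 2.3 points at RR 0.8.

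**6. A side check on Table B.** The column for p<0.05 at the second interim is printed as 0.0 in all nine rows. Re-simulation gave 2.0% and 2.3% at RR 1.333.

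**The case against.** The other side has four fair points.

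- **It is disclosed.** Appendix C states the inflation and prints the numbers. The disagreement is over whether 0.4 points of one-sided alpha can be tolerated. That stands as to candour, but section 2.10 still pairs 78% with 0.025, and the cause given would steer a reader away from the remedy.
- **The absence of a correction is inferred.** The plan never says that none is used. The inference rests on no correction being named and on the uncorrected version matching Table B, with an assumed number of sites. This stands as a caveat.
- **76–77% is no more the true power than 78% is.** Both assume covariates unrelated to outcome, while section 2.16 expects strong predictors. With two prognostic covariates (assumed log RR 0.4 per SD each), a corrected analysis gave 80.3% power and 2.6% false benefit. The restated figure is therefore conditional on Appendix C's assumption and should be labelled so.
- **Benefit-row coverage is mostly a stopping effect.** A reader might infer from the 91–93% that the sandwich makes intervals too optimistic just where benefit would be claimed. Table B does not support that. Much of the shortfall comes from trials halted with an estimated RR above 1.1, and those intervals err toward harm.

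Two further inferences fail. A reader might suppose that an interval reported at the first interim would rest on about 14 pilot sites; the documents do not give the site mix of the first 222 patients, and a trial stopped there claims no benefit. A reader might also suppose that harm-only stopping masks a larger inflation; Table B shows 0.0% of null runs losing a significant benefit to stopping, and re-simulation shows only 2.98% falling to 2.94%.

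**Conclusion.** The point holds on the protocol's own figures: as simulated, 78% power goes with a one-sided error of about 0.029, and null coverage is 94%. The probable cause is the site-clustered sandwich with a modest number of clusters and apparently no small-sample correction, not modified Poisson or robust standard errors in general. That attribution rests on re-simulation with about 40 assumed sites.

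The effect is small: about 0.4 points of one-sided alpha and 1–2 points of power. It does not show that the trial is too small. The simple Wald calculation in step 1 and the non-clustered robust analysis both give about 78% at close to 0.025. What needs correcting is the match between the chosen variance, its error rate and the stated power. A correction brings null coverage to about 95% when there is no early stopping. In the benefit rows it lifts coverage only from about 91–92% to about 93%.

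**What to change.** - **Section 2.16:** specify a small-sample-corrected site-clustered variance for the primary and binary secondary outcomes, for example G/(G−1) with a t reference on sites−1 df, or Mancl-DeRouen with a normal reference. Choose one: Mancl-DeRouen with a t reference overcorrects (2.3% false benefit, 74.7% power).
- **Appendix C:** re-run Table B with that variance, state the number and sizes of the simulated sites, amend the explanation of the inflation, and say that part of the under-coverage in the benefit rows comes from the stopping rule. Check the second-interim p<0.05 column in the same run.
- **Section 2.10:** restate power with the resulting figure, about 76–77% under non-prognostic covariates.

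The cost is a sentence in the analysis plan, one re-run of an existing simulation, and a stated power 1–2 points lower. Patients, visits and data collection are unaffected.

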Appendix D: SAE and causality/relatedness definitions

A **Serious Adverse Event (SAE)** is defined as any untoward medical occurrence that at any dose:

- Results in death.
- Is life-threatening (refers to an event in which the study participant was, in the opinion of the qualified investigator (QI), at risk of death from the event if medical intervention had not occurred. NOTE: This does not include an event that hypothetically had it occurred in a more serious form, might have caused death).
- Requires inpatient hospitalization or prolongation of existing hospitalization.
- Results in persistent or significant disability/incapacity (i.e. a substantial disruption in an individual's ability to conduct normal life functions).
- Is a congenital anomaly or birth defect.
- Other medically important condition (Important medical events that may not result in death, be life-threatening, or require hospitalization may be considered serious events when, based on medical judgment, they may jeopardize the patient and may require medical or surgical intervention to prevent one of the outcomes listed above).

Relationship of Study Intervention to event (The determination of the relationship of the SAE to the investigational product must be made by the Site Investigator or trained sub-Investigator. To assist the Investigator in making this assessment, the following definitions have been provided (select **only** one):

- **Not related:** A serious adverse event that is clearly due to extraneous causes (disease, environment, etc.) and does not meet the criteria for drug relationship listed under 'Possibly' or 'Probably'.
- **Unlikely related:** A serious adverse event that is more likely due to other causes than the study intervention.
- **Possibly related:** Suggests that the association of this SAE with the study intervention is unknown and the event is not reasonably supported by other conditions.
- **Probably related:** Suggests that a reasonable temporal sequence of this SAE with study intervention administration exists and the association of the event with the study intervention seems likely.

If the SAE is considered to be related to the investigational product, please provide the pertinent clinical features that, in the opinion of the Investigator, made her/him think that the event was related to the study intervention vs. the progression of underlying disease.

References

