2.20 Serious Adverse Events and Safety Reporting

In the context of an acute critical illness, all patients eligible for the VICToRY Trial are at risk of adverse events (AEs). Following Canadian guidelines for AE reporting in academic critical care trials, expected AEs were pre-specified as trial outcomes and will not be reported as AEs. These events will be recorded in the electronic data capture system as part of data collection. No other AEs will be reported.

Patients will be monitored daily for SAEs. Clinical sites will document all unexpected SAEs in the EDCS. The local principal investigator, with support from the trial principal investigators and Coordinating Centre, will determine if the SAE is possibly related to the study intervention (see Appendix D for SAE and causality/relatedness definitions). The trial principal investigators and Coordinating Centre will also support the local principal investigator with

determining if the SAE is unexpected. Unexpected SAEs must be reported to the Coordinating Centre via the EDCS within 24 hours of the local principal investigator becoming aware of the unexpected SAE. Unexpected SAEs that are considered to be possibly related to the trial intervention will be reported to all applicable regulatory authorities and participating site principal investigators by the Coordinating Centre in an expedited manner. Clinical sites are also responsible for reporting SAEs to the Institutional Review Board (IRB)/Research Ethics Board (REB) of record as per their IRB/REB of record's reporting requirements.

In accordance with Health Canada requirements for reporting suspected unexpected serious adverse reactions (SUSARS), the Coordinating Centre will inform all applicable regulatory agencies of any unexpected SAEs that are possibly related to the trial intervention within 15 days (if it is neither fatal nor life threatening), or within 7 days after becoming aware of the information (if it is fatal or life threatening). AEs and SAEs that are expected, but not serious, will not be reported to regulatory agencies, but rather monitored and tracked by the Coordinating Centre. The Coordinating Centre will report to applicable regulatory agencies "expected" SAEs, where an increase in the rate of occurrence or severity, was judged to be clinically important.

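### Appendix D bars an SAE from being possibly related when another cause reasonably explains it, so some suspected unexpected reactions may miss expedited reporting

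*Combined protocol and SAP*

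**What the plan says.** Appendix D gives four relatedness categories for an SAE and tells the investigator to choose one only:

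- *Not related*: "A serious adverse event that is clearly due to extraneous causes (disease, environment, etc".) and meeting neither the possibly nor the probably criteria.
- *Unlikely related*: "A serious adverse event that is more likely due to other causes than the study intervention".
- *Probably related*: the timing is plausible and "the association of the event with the study intervention seems likely".
- *Possibly related*, the category at issue here: "Suggests that the association of this SAE with the study intervention is unknown and the event is not reasonably supported by other conditions".

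Section 2.20 refers to Appendix D for these definitions and builds its reporting rule on one of them: "Unexpected SAEs that are considered to be possibly related to the trial intervention will be reported to all applicable regulatory authorities", and also to the investigators at participating sites. The same term starts the Health Canada clock of 15 days, or 7 days if the event is fatal or life threatening. Expectedness is a separate filter: "expected AEs were pre-specified as trial outcomes and will not be reported as AEs".

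**The concern.** A threshold for suspected reactions should catch events that the drug may have caused, including those that something else may also have caused. Here the second half of the definition works the other way, because a reasonable competing explanation removes the event from the category that triggers the report.

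Competing explanations are to be expected in this population. Section 1.3 describes burn shock, systemic inflammation and progressive organ dysfunction as consequences of the injury itself. Section 1.5, citing single case reports of metabolic acidosis with vitamin C, says that they arose when several derangements were present together. Mixed causation is thus a pattern that the protocol itself describes.

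At stake is whether a single unexpected SAE of ambiguous cause reaches regulators and the other sites promptly as a suspected reaction. The efficacy analysis is not affected.

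**Working it through.** No arithmetic applies. The documents give no SAE count, relatedness rate or expected number of expedited reports. The check is to take an unexpected SAE and see where each combination of explanations falls under Appendix D, and what section 2.20 then does with it.

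| Judgement on cause | Category under the literal wording | Expedited under section 2.20? |
|---|---|---|
| A. No other reasonable cause, drug association unknown | Possibly | Yes |
| B. Drug association judged likely, burn also a reasonable cause | Probably | Only if the threshold is read as possibly or higher, which section 2.20 does not state |
| C. Drug and burn about equally plausible | None fits | Not triggered |
| D. Burn judged more likely than drug | Unlikely | No |

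**Case C, category by category.**

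1. Not related fails, because the event is not clearly due to something else.
2. Unlikely fails, because no other cause is more likely than the drug.
3. Possibly fails, because the burn reasonably supports the event. The two conditions are joined by *and*, so failing one is enough.
4. Probably fails, because the drug association is uncertain rather than likely.

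The investigator must still select one category, and the text does not say which to use.

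**Order of the scale.** A competing burn explanation is allowed in B, under probably, but not under possibly. On alternative causes the lower category therefore asks for more than the higher one.

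**Do other routes start the regulatory clock for case C?**

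- *Coordinating Centre.* It receives every unexpected SAE within 24 hours, whatever the relatedness (section 2.20). Its own duty to inform agencies uses the same possibly related test. It and the trial principal investigators support the local decision, but no power to upgrade a site's causality rating is stated.
- *DMC.* It reviews all SAEs and may call an ad hoc review when two or more similar ones cause concern (section 1.5). That is not a regulatory report on a single event.
- *Ethics boards.* SAEs go to them under each board's own requirements (section 2.20).
- *Rise in rate or severity.* This route to the agencies covers expected SAEs only (section 2.20).

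None of the four starts the 7- or 15-day clock for one ambiguous unexpected event.

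**After the proposed rewording.** Case C becomes possibly related and is expedited. Case B is expedited explicitly. Cases A and D are unchanged.

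**The case against.** The strongest defence has four parts.

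1. *The definitions are aids to judgement.* Appendix D offers them to assist the investigator. It closes by asking, for a related event, why the investigator attributed it to the intervention and not to progression of the underlying disease. That request assumes that related events can have a disease explanation. This is a fair point about intent, and many sites may read the scale sensibly. It does not repair the definition, which says the opposite for the category that matters.

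2. *Probably related remains open.* It does not require other causes to be absent. Appendix D also groups possibly and probably together when it defines not related, so possibly or higher is the natural threshold. This stands. It covers case B but not case C.

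3. *Expectedness may decide first.* Expedited reporting applies only to unexpected SAEs. Acid-base and electrolyte imbalance, hemolysis and hypoglycemia are named risks in section 1.5 and appear among the events of interest in Appendix B. Kidney injury is followed as an outcome. The available text has no list of expected SAEs, so their status is uncertain, but they may leave this route before relatedness is considered. Severe acidosis during burn shock is therefore not a safe example of a lost report.

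4. *Other oversight exists.* The routes listed above are real, and kidney injury and renal replacement are also reviewed by group each year. They limit the consequence without replacing the regulatory trigger.

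A reader might go further and infer that, in severe burns, hardly any SAE could qualify and expedited reporting is in effect switched off. The documents do not support that. No figure lies behind it, probably related is still a route, and the unexpected events left after the expected ones are removed may be less readily explained by the burn.

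**Conclusion.** The wording defect is real and limited. Applied literally, Appendix D excludes from possibly related any SAE with a reasonable alternative cause, reverses the order of possibly and probably on that point, and leaves evenly balanced events without a category. Because section 2.20 uses the term as its threshold, some suspected unexpected reactions with a competing burn explanation may not be reported to regulators and sites.

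The affected set is the unexpected SAEs in case C, plus those in case B if section 2.20 is read as meaning possibly only. Its size cannot be derived. The conclusion rests on sites applying the definition as written and on the event having been judged unexpected. Nothing in the documents shows that any event has been misclassified so far, and nothing suggests that the DMC or the Coordinating Centre would fail to see these events. The change is worth making because it is cheap and bears on patient safety.

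**What to change.** 1. In Appendix D, redefine possibly related: a causal relationship with the study intervention is a reasonable possibility and cannot be excluded, even if the injury or other conditions could also explain the event.
2. Keep unlikely related for events where another cause is more likely, and say that it applies only then, so that evenly balanced events fall under possibly and no event fits two categories.
3. In section 2.20, state that unexpected SAEs rated either possibly or probably related trigger expedited reporting and the 7- or 15-day clock.
4. Re-check, blinded to allocation, the relatedness of any unexpected SAEs already recorded. This is a precaution. The documents do not say how many there are.

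The cost is a wording amendment in two places, a memo to sites, the re-check, and somewhat more expedited reports from now on. Treatment, endpoints, sample size and analysis do not change.
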